4.3.6 Anorectal manometry. Determine anal resting and anal squeeze pressures, sphincter squeeze endurance, rectal sensory thresholds (bag volume and intra-bag pressure at the first report of sensation, desire to defecate, urgency to defecate, and maximum tolerable volume), and rectal compliance. These parameters will be measured at baseline (but can be measured prior to randomization if not measured at Baseline) and may also be done at 3 months following initial treatment using the portable Medspira Anorectal manometry equipment, which can be used in the office and does not require a dedicated laboratory. This system includes a catheter, with 4 radially-oriented equidistant anal balloons and 1 rectal balloon, a wireless manometer, and a computer. The catheter is connected to the manometer that has pressure transducers and communicates wirelessly to the computer. The acquisition module display provides instructions that guide users conducting the study. The maneuvers used during portable manometry are identical to those in high-resolution manometry (HRM). Anorectal pressures and rectal sensation measured with portable manometry are significantly correlated with high-resolution manometry. Participants who initially respond to EMM but are then randomized after they are identified as non-responders at the 3-month follow-up visit may have the ARM performed at the initial 3-month assessment but it should not be repeated at their second 3-month follow-up assessment if they are then randomized to BIO or INJ.

4.3.7 Motor evoked potentials (MEP) will be tested at the Baseline visit (but can be tested at any time before randomization). It may also be tested at 3-month follow-up in all treatment groups. However, participants who initially respond to EMM but are then randomized after they are identified as non-responders at the 3-month follow-up assessment will not have the MEP repeated at their second 3-month follow-up assessment, that is, at the follow-up 3 months after they initiated the randomized treatment. The MEP data will be collected at the Mayo Clinic and Augusta University. MEP data will not be collected at the University of North Carolina at Chapel Hill, the University of Alabama at Birmingham, and the University of Michigan.

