This test uses a specially designed rectal probe with 2 pairs of bipolar steel ring electrodes, each 2 cm apart, mounted on a catheter (Gaeltec Ltd, Isle of Skye). The proximal pair will be located 8-10 cm from anus and the distal pair at 1-2 cm from anus. The electrodes are used to record the motor evoked potentials after magnetic stimulation. Magnetic stimulation of the lumbar (TLMS) and sacral (TSMS) nerve roots will be performed using a commercially available 90 mm coil magnetic stimulator (Magstim 200^2; MAGSTIM, Whitland, UK). The subject will lie prone. For the TLMS study, the coil will be placed on each side of the midline approximately 3-5 cm laterally and between L2 and L3 vertebra. The coil will be discharged with increasing frequency starting at 50% and up to a maximum output of 85% of the scale range for magnetic stimulation intensity. For the TSMS test, the sacrum will be palpated to identify the S2 and S3 vertebra. The coil will be placed on each side of the midline over the sacrum (S2-S3) and discharged up to a maximum of 85% magnetic stimulation intensity. The EMG responses from anterior tibialis muscle of one leg will also be recorded (as a control) using Ag/AgCl disc electrodes The MEP responses will be recorded into a 4-channel amplifier with a built in AD interface (Nihon Kohden, Japan) with filter settings of 5-2000 Hz and at a sampling rate of 4-8 kHz, fed into a computer for display and analysis. Figure 3 shows the whole system. An optimal response will be defined as an anal and rectal MEPs of >10µV and tibialis response of 100µV on at least 3/6 consecutive trials. A rest period of 5 minutes will be allowed between stimulations on each side. Five MEP responses will be obtained on each side and the average of the best three responses will be used to measure MEP response.

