Measurements and Analysis: The latencies of wave forms (Figure 2) on both the TLMS and TSMS-induced MEP responses will be analyzed on both the right and left sides. The first and most prominent negative or positive deflection will be designated as the MEP response. We will measure the average latency for the left lumbo-rectal and lumbo-anal and the right lumbo-rectal and lumbo-anal MEPs. Similarly, the average latency for the left sacro-rectal and left sacro-anal and the right sacro-rectal and right sacro-anal MEP responses will be measured for a total of 8 measures. Each averaged response latency will be classified as abnormal if it is greater than the upper confidence interval reported previously for healthy controls; otherwise normal. Patients will be classified as having a neuropathy if  $\geq$ 1 of 8 average latencies are abnormal. The validity of this test as a measure of pelvic nerve neuropathies was demonstrated in previous studies showing that these latencies differentiate patients with FI as a group from healthy controls (abnormally delayed latencies in 80% of patients with FI), and abnormally delayed latencies are also found in patients with spinal cord injury (known neuropathy)

Figure 2. Typical motor response to magnetic stimulation of the lumbar spine

4.3.8 Anorectal ultrasound or pelvic floor MRI. Measured at baseline (but if not done at Baseline, can still be measured up to and including at the time of the Randomization visit) in all subjects and may also be done at 3 months in dextranomer treated patients. Sites will report who performs and interprets the test, whether an anorectal ultrasound or a pelvic floor MRI was performed, the person performing the test and the person interpreting the study, the width of any defects in the internal and external anal sphincters and puborectalis muscles, and the minimum thickness of these muscles. For sites using anorectal ultrasound, BK probes that are 3 dimensional will be used, except for The University of Alabama at Birmingham where 2 dimensional BK probes will be used. Please see the Anorectal ultrasound/pelvic floor operating procedure manuals. If this was performed in the previous 12 months to assess the sphincters, then this need not be repeated at Baseline if the sphincters appeared normal and there has been no history of anorectal trauma, surgical procedures, or vaginal deliveries in the intervening period between the imaging exam and study participation.

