#### 8.3 Analysis of Secondary Aims

*Identify predictors of treatment response to each intervention.* Generalized linear modeling will be used to identify baseline variables which are significant independent predictors of responder status at 3 months. Candidate independent variables in these models include (a) demographic variables (e.g., sex, age, race, ethnicity, education); (b) clinical history variables (e.g., FI frequency, volume, duration, and association with urgency and diarrhea); and (c) baseline pelvic floor physiology (e.g., anal canal resting pressure, squeeze pressure, duration of squeeze, rectal sensory threshold for first sensation and urgency, maximum tolerable volume, structural integrity of anal sphincters assessed by ultrasound, and integrity of the pelvic floor innervation by trans-sacral and trans-lumbar magnetic evoked potentials) and other moderator variables described in the protocol. Differences in predictors of response among the treatment groups will be assessed by evaluating interaction terms for the predictors and treatment group. Secondary analyses evaluating predictors of treatment response at other time points and predictors of other secondary outcomes will be conducted using similar methods.

Investigate the mechanistic basis for treatment success for each intervention. General linear modeling will be used to identify measures associated with change from baseline to 3 months in FI frequency. The independent variables to be tested are anal squeeze pressures, rectal sensory thresholds, rectal maximum tolerable volume, trans-lumbar and trans-anal magnetic evoked potential, stool consistency measure by the Bristol Stool Form Scale, and adherence to protocol. Differences in predictors among the treatment groups will be assessed by evaluating interaction terms for the predictors and treatment group.

*Evaluate treatment combinations.* To assess the effectiveness of allowing non-responders to choose an additional treatment at 3 months, we will estimate 95% confidence intervals for the number of responders in each treatment-order combination at 6, 12, and 24 months using a Wilson Score interval. Confidence intervals will be compared descriptively.

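### The one-of-eight MEP neuropathy rule over-calls healthy nerves by an amount the plan leaves open, and an absent response can never count as abnormal

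*Combined protocol and SAP*

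**What the plan says.** Section 4.3.7 (under 4.3 Moderator variables) takes latencies after lumbar and sacral stimulation, at rectum and anus, left and right: "MEP responses will be measured for a total of 8 measures". Each one is then classed: "Each averaged response latency will be classified as abnormal if it is greater than the upper confidence interval reported previously for healthy controls; otherwise normal". The patient has a neuropathy if at least "1 of 8 average latencies are abnormal".

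The only performance figure offered is "abnormally delayed latencies in 80% of patients with FI". No positive rate for healthy controls under the same rule is given.

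On recording, an optimal response needs anal and rectal potentials above 10 µV and a "tibialis response of 100µV on at least 3/6 consecutive trials". The next lines say: "Five MEP responses will be obtained on each side and the average of the best three responses will be used to measure MEP response".

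On coverage: "The MEP data will be collected at the Mayo Clinic and Augusta University". The other three sites do not collect MEP data.

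Section 8.3 lists as a candidate predictor of response, to be tested also for interaction with treatment, the "integrity of the pelvic floor innervation by trans-sacral and trans-lumbar magnetic evoked potentials". The mechanistic analysis in the same section lists the evoked potential as well. Neither entry says whether the yes/no class or the latencies go into the model.

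**The concern.** There are two separate problems.

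**Over-calling.** Each person gets eight chances to exceed a limit, and one exceedance decides the label. Unless the latencies are perfectly correlated, the patient-level false-positive rate is higher than the per-latency rate. The limit itself is also unclear. A confidence limit describes where the mean of controls lies, so a large share of healthy individuals would fall above it. If a reference limit for individuals is meant, its percentile and source are missing.

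**Absent responses.** The label can be triggered only by a latency that was measured and found long. A patient with an adequate tibialis control but no recordable anorectal response at the maximum 85% output has no latency at that site, and the plan gives no code for this.

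Aim C and section 8.3 ask whether innervation predicts response to BIO or INJ. The yes/no class is the only patient-level MEP summary that 4.3.7 defines. If it is used, false positives dilute the contrast between classes. Leaving the form of the predictor open also invites a choice made after seeing the data.

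**Working it through.** **Inputs from the documents:** 8 latencies; neuropathy if at least 1 is abnormal; 80% of FI patients abnormal; MEP at 2 of 5 sites; 97 randomized per arm.

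**Assumptions (not in the documents):** normally distributed latencies with a common correlation ρ; the level and kind of limit; for the literal reading, the number of controls n.

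The 80% cannot be reproduced, because the plan gives no counts, cut-off level, control n or control rate.

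**Step 1. Individual reference limit, independent latencies.**
- 97.5th percentile: 1 − 0.975^8 = 18.3%.
- 95th percentile: 1 − 0.95^8 = 33.7%.

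**Step 2. Correlated latencies.** With cut-off c in SD units, P(at least 1 of 8) = 1 − ∫ φ(u) · Φ((c − √ρ·u)/√(1−ρ))^8 du.

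| Limit | Per latency | ρ=0 | ρ=0.5 | ρ=0.8 | ρ=0.9 |
|---|---|---|---|---|---|
| 97.5th percentile | 2.5% | 18.3% | 12.5% | 7.9% | 6.0% |
| 95th percentile | 5% | 33.7% | 21.9% | 14.1% | 10.9% |

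Even at ρ=0.9 the patient-level rate is more than twice the per-latency rate.

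**Step 3. Literal reading, upper 95% confidence limit of the control mean.** The limit lies 1.96/√n SD above the mean, so the per-latency rate is 1 − Φ(1.96/√n).

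| Controls | Per latency | ρ=0 | ρ=0.5 | ρ=0.9 |
|---|---|---|---|---|
| n=10 | 27% | 92% | 68% | 43% |
| n=20 | 33% | 96% | 75% | 51% |
| n=50 | 39% | 98% | 81% | 57% |

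**Step 4. What limit would hold the patient-level rate at 5%?** For independent latencies, 1 − 0.95^(1/8) = 0.64% per latency, or z = 2.49. The plan does not claim so strict a limit.

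**Step 5. Effect among FI patients.** Let f be the healthy false-positive rate, and suppose sensitivity is perfect and 80% test positive. True prevalence is then (0.80 − f)/(1 − f).
- f = 2.5%: 79%.
- f = 18.3%: 76%.
- f = 33.7%: 70%.

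A difference in response rate between true classes shrinks by PPV + NPV − 1. With perfect sensitivity NPV is 1, so the factor equals PPV: 0.755/0.80 = 0.94 at f = 18.3%, and 0.698/0.80 = 0.87 at f = 33.7%.

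**Step 6. Absent responses.** The documents give no frequency. As an illustration only, take a true prevalence of 80% and suppose that 5%, 10% or 20% of all patients have an absent response as their only sign and are coded not neuropathic. Sensitivity is 1 − 0.05/0.80 = 94%, 1 − 0.10/0.80 = 88%, or 1 − 0.20/0.80 = 75%.

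**Step 7. Data available.** With equal enrolment by site (assumed), 194 × 2/5 = 77.6 randomized patients have MEP, or 97 × 2/5 = 38.8 per arm. At 80% positive, 38.8 × 0.20 = 7.8 per arm are classed normal.

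**The case against.** The case on the other side is substantial, and much of it stands.

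- **The limit.** The wording may be a loose name for a reference limit. The same paragraph says the latencies separate FI patients as a group from healthy controls, and a rule flagging nearly all controls would sit badly with that. The 92% to 98% figures also need independence, which is implausible for left and right, anal and rectal readings in one person. This stands: the reference-limit rows are the ones to rely on. It does not remove the eight comparisons or supply the percentile.
- **Two-way misclassification.** A reader might infer that the predictor is misclassified in both directions. The documents do not support this. The default to normal applies to an averaged latency, which an absent response does not have, so missing is at least as natural a reading. Another delayed latency among the eight would still flag the patient. The 10 µV criterion defines an optimal response and does not say that a smaller one has no latency. A procedure manual may also cover the case.
- **The model.** Section 8.3 does not commit to the yes/no class. If the latencies are used, the cut-off problem disappears, though the absent-response problem does not.
- **About 8 per arm classed normal.** A reader might blame the rule for this. A perfect test at 80% prevalence would give the same number.
- **Three of six trials against five responses.** A reader might call this a contradiction. One passage defines an optimal response and the other the number of responses collected, so this is a minor point to reconcile.
- **Stakes.** No primary endpoint or sample size depends on MEP, and the version 5.0 change rationale says it is not a core procedure.

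**Conclusion.** The concern holds as a defect of specification and method in a secondary predictor. The one-of-eight rule inflates the false-positive rate: roughly 8% to 18% of healthy people at a 97.5th percentile limit and 14% to 34% at a 95th, for assumed correlations of 0.8 to 0. A literal confidence limit of the mean would label about half or more with 20 or more controls, even at correlation 0.9. The true figure is unknown because the level, control n and correlations are not in the documents, and a limit near z = 2.5 would keep it at or below about 5%.

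Within the FI sample the dilution from over-calling alone is modest: a factor of 0.94 or 0.87 in the Step 5 cases, which assume perfect sensitivity. An absent response can never count as abnormal. That gap is certain, but any under-call depends on unstated coding and cannot be sized from the documents. The reach is limited to the secondary predictor and mechanism analyses with MEP data from two of five sites. The change is still worth making, because Aim C is a named aim and the latencies are already recorded.

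**What to change.** In 4.3.7 and 8.3:

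1. Make a continuous summary of the recorded latencies the primary MEP predictor, for example the mean of latencies standardized within the trial sample, or to healthy controls if their means and SDs are available. Keep the yes/no class as descriptive.
2. State that the cut-off is an upper reference limit for individuals, and give its percentile and source.
3. Prespecify that a technically adequate test with no recordable response is kept apart from a technical failure and is not counted as normal, for example through an indicator or a rank-based score. Say how one absent site among eight is handled.
4. Reconcile the three-of-six-trials criterion with the five responses collected, and define which three responses count as best.

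The cost is protocol and SAP wording plus a little more analysis work. No new test and no patient burden is added. Comparability with earlier yes/no reports is slightly lower for the main predictor, and the descriptive class covers that.

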It could be argued that, even if BIO were to be equally effective as INJ of dextranomer, it would be logical to try BIO first because it is safer, and to only use INJ in those who fail BIO. In practice, however, there is no consistent standard for defining BIO or judging what "failing biofeedback" means. If the proposed comparative effectiveness study shows that BIO is equally effective or more effective than INJ, treatment algorithms and insurance reimbursement policies may need to be re-evaluated. An outcome such as this might also stimulate research into whether treatment combinations may be more consistently effective than trying these treatments one at a time.

An NIDDK Workshop hosted in 2014 addressed research priorities for FI and concluded that the highest priority for research should be "trials comparing the effectiveness, safety, and cost of current therapies". Such a comparative effectiveness study needs to be performed at multiple sites because (1) the number of patients currently referred for these treatments is relatively small at individual medical centers, (2) FI is a multi-faceted disorder and patient phenotypes may differ among centers, and (3) the success of BIO varies across clinical settings and is known to be influenced by the training and experience of the therapist.

Outcome Domain	BIO	INJ	SNS	
Efficacy (success rated by authors' definition)	55%  - 93% 	53% 	83% 	
Efficacy (>75% decrease in FI frequency)	78% 	32% 	56% 	
Continence (%)	5%  - 44% 	5.9% 	25%  - 40% 	
Adverse events (pain or infection)	0% 	10% 	6%  -11% 	
Reimbursement (range in US \$)	\$1,235 – 2,300	\$3,000 - 7,408	\$29,000 - 69,000	

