## 5.2 Sample Size Estimates

## 5.2.1. Primary Efficacy Outcome

Sample-size calculations are based on the number of patients required to detect a difference of 20% in the proportion of responders because we consider this to be the Minimum Clinically Important Difference (MCID) between groups following treatment. Table 3 shows the sample data used in these calculations, which comes from published pivotal trials for dextranomer and biofeedback. Conservatively assuming an average response rate of 50% across the groups, an alpha of .05 and power of 80% we would need at least 97 patients per group to test for differences of this magnitude between 2 treatment groups. Since the planned analysis will use an intention to treat (ITT) approach in which all participants will have a defined efficacy outcome regardless of study completion, this sample size was not inflated to account for potential drop out.

The data in Table 3 suggest that we have an excellent chance of detecting a difference of 20% and of showing that BIO is superior to INJ in the proposed trial. We should also be able to show significant differences between BIO and the other two treatments for adverse events, estimated cost of care, percent continent, and impact of FI on quality of life (Table 4).

Efficacy Outcome Measure	BIO Heymen 	INJ Graf 	Sample size required per group
Baseline: FI days per week	3.4 (SD=2.1)	4.8	
> 50% decrease (%)	93%	53%	28
> 75% decrease (%)	78%	32%	28
Continent (%)	44%	5.9%	29

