## 7.0 Randomization and Masking

#### 7.1 Randomization

Enrollment in the study will be defined as satisfying all eligibility criteria and signing informed consent (see Section 9.4). Randomization to the two interventions being compared BIO and INJ) will not occur until patients have completed EMM and been classified as a non-responder based on showing a less than 75% reduction in the average frequency of solid, liquid, and/or staining FI events compared to the two-week baseline. See Figure 4 for Decision Tree governing patient flow through the study.

Randomization will occur in a ratio of 1:1 with an equal chance of being randomized to each treatment group. Randomization will be performed using randomly permuted blocks, with block sizes known only to the DCC, and will be stratified by clinical site and sex (male and female). For each participant, the web-based electronic data capture system will determine the treatment allocation from a static randomization table. Personnel at the clinical sites will not have access to the randomization table in order to minimize the risk of selection bias.

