## 8.0 Statistical Considerations

## 8.1 Analysis of Primary Endpoints

Assessment of Randomized Treatment Response at 3 Months (Primary Efficacy Analysis). To test the efficacy of randomized treatment assignment, a generalized linear model with a logit link will be constructed to predict treatment response at 3 months post-randomization. Treatment group and the stratification factors of clinical site and sex will be included in the model as categorical independent variables. An ITT approach will be used in which participants will be analyzed based on their assigned treatment group regardless of actual treatment received. Participants without a valid bowel diary at 3 months due to drop out or other reasons will be classified as non-responders. Using this model, we will test the null hypothesis that the proportion of responders is the same in the two treatment groups at 3 months following randomization using an alpha of 0.05. Sensitivity analyses will be conducted to assess the impact of classifying participants with missing data as non-responders.

Assessment of Safety. The primary safety outcome is the percentage of participants in each randomized treatment group who experience an adverse event (AE) of pelvic pain of grade II or greater severity, treatment site infection, or a serious adverse event (SAE) requiring hospitalization between randomization and the 3 month assessment. Because the proportion of participants with one of these events is expected to be small, Fisher's exact tests will be used to compare the percentage of participants with a qualifying adverse event. The difference between the two treatment groups will be evaluated for significance using an alpha of 0.05. Participants who are missing safety data due to drop out or other reasons will be excluded from this analysis.

*Cost of Care Analysis.* Mean and median costs per participant will be estimated for each of the two treatment groups and from the perspectives of payers, patients, and society. We will analyze whether differences in costs through 3-month follow up across the intervention arms and perspectives are statistically significant using parametric t-tests or using non-parametric bootstrapping methods. We will evaluate differences between the two treatment groups using an alpha of <0.05.

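### The predictor and mechanism models in Section 8.3 do not name clinical site, so a site difference in response could be read as the effect of a patient measure that also varies by site

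*Combined protocol and SAP*

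**What the plan says.** **Section 8.3, predictor model.** A generalized linear model is to identify significant independent predictors of responder status at 3 months. Candidates are demographics, clinical history, baseline pelvic floor physiology (including sphincter structure on ultrasound) and the protocol's other moderators. The list is illustrative. Site is not on it, and it is not among the moderators in Section 4.3, although sex is. Predictors are compared between arms through predictor-by-treatment interactions.

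**Section 8.3, mechanism model.** The outcome is change in FI frequency to 3 months. The list is closed: "The independent variables to be tested are anal squeeze pressures, rectal sensory thresholds, rectal maximum tolerable volume", then evoked potentials, stool consistency and adherence. It contains neither site nor sphincter imaging.

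**Elsewhere.** In Section 8.1, "Treatment group and the stratification factors of clinical site and sex will be included in the model as categorical independent variables". The FI severity model in Section 8.2 also names site, as does the EMM durability model in Section 8.3.

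**Why site may matter here.** Section 2.1 justifies a multisite trial partly because patient characteristics may not be alike across centers, and because "the success of BIO varies across clinical settings and is known to be influenced by the training and experience of the therapist". Section 4.3.8 allows ultrasound or MRI and specifies 3-D probes "except for The University of Alabama at Birmingham where 2 dimensional BK probes will be used".

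**The concern.** A variable confounds a predictor-response association when it is linked to both. The protocol gives grounds for both links: patient mix may vary by center, and so may biofeedback success. A model without site attributes any between-site difference in response partly to whichever measures happen to differ between the same sites. A measure could then qualify as an independent predictor although, among patients at one site, it says nothing about response.

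Aim C is meant to identify which patients respond to which treatment. A predictor that only marks where a patient was treated would not help a clinician at any single center choose between biofeedback (BIO) and injection (INJ).

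**Working it through.** **1. Sample size available to these models.** The plan sets out to "detect a difference of 20% in the proportion of responders" ("Conservatively assuming an average response rate of 50% across the groups, an alpha of .05 and power of 80" percent) and concludes that "we would need at least 97 patients per group". Section 7.1 adds: "Randomization will occur in a ratio of 1:1". With 40% versus 60%, two-sided alpha 0.05 and pooled variance:

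n = [1.960 × √(2 × 0.5 × 0.5) + 0.8416 × √(0.4 × 0.6 + 0.6 × 0.4)]² / 0.20² = (1.3859 + 0.5831)² / 0.04 = 96.9, so 97 per group.

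The plan's figure is reproduced and is not in dispute. It gives N = 194 at 5 sites. The plan states no figure for the predictor or mechanism models.

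**2. How the bias arises.** Take a yes/no finding with prevalence aₛ and response rate rₛ at site s, equal site sizes, and no association within any site. Pooling over sites:

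P(response | finding) = Σaₛrₛ / Σaₛ

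P(response | no finding) = Σ(1 − aₛ)rₛ / Σ(1 − aₛ)

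- One site differs in both (finding 15% vs 30%, response 30% vs 55%): 0.705/1.35 = 0.522 vs 1.795/3.65 = 0.492, odds ratio 1.13.
- Mild gradient over all sites (finding 20-40%, response 40-60%): 0.775/1.5 = 0.517 vs 1.725/3.5 = 0.493, odds ratio 1.10.
- Moderate gradient (finding 10-50%, response 30-70%): 0.85/1.5 = 0.567 vs 1.65/3.5 = 0.471, odds ratio 1.47.

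If either aₛ or rₛ is constant, the two rates are equal and the odds ratio is 1. All site inputs are assumptions.

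**3. False-positive rate, yes/no finding.** 3,000 simulated trials per row, N = 194, 5 equal sites, treatment in every model, nominal 5%.

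| Assumed site differences | Without site | With site | Odds ratio without / with site |
|---|---|---|---|
| Finding only | 4.9% | 4.8% | 1.01 / 1.00 |
| Response only | 4.9% | 5.1% | 0.99 / 0.99 |
| One site, both | 6.7% | 5.2% | 1.14 / 1.01 |
| All sites, mild | 7.2% | 6.4% | 1.11 / 1.00 |
| All sites, moderate | 22.8% | 5.3% | 1.49 / 1.01 |

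The simulated odds ratios agree with step 2. The Monte Carlo standard error near 5% is √(0.05 × 0.95 / 3,000) = 0.4 points.

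**4. False-positive rate, continuous measure.** 3,000 trials per scenario, sites of 50/45/40/32/27.

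| Predictor variance between sites | Site SD in response | Without site |
|---|---|---|
| 20% | 10 points | 7.5% |
| 20% | 15 points | 11.9% |
| 40% | 10 points | 10.9% |
| 40% | 15 points | 17.2% |
| 20% or 40% | 5 points | 4.7-6.1% |

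With site in the model the range is 4.6-6.1%.

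**5. Predictor-by-treatment interaction.** Same site sizes, with a site effect of SD 15 points in the BIO arm only. With 20% and 40% of predictor variance between sites, the false-positive rates are:

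- no site term: 6.8% and 8.4%;
- site main effect only: 7.0% and 8.7%;
- site-by-treatment added: 5.8% and 5.3%.

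A site main effect alone therefore does not protect the interaction test.

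Steps 3-5 use responder status as the outcome. For the mechanism model, whose outcome is change in FI frequency, they show the direction but not the size.

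**The case against.** **Site is unspecified, not excluded.** The predictor candidates are examples, and both lists name variables under test; neither is said to be the full set of covariates. This stands. But where site is intended, Sections 8.1 and 8.2 and the EMM durability model name it, and here they do not.

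**A reader might infer that mixing 3-D, 2-D and MRI imaging by itself biases the predictor results, and in both models.** The documents do not support that. The mechanism list has no sphincter imaging. Nothing in the protocol shows that the methods give different readings, and Section 4.3.8 defers to operating manuals not included here. When only the finding differs by site, the false-positive rate is 4.9%. When one site differs in both finding and response, it is 6.7%. Imaging is one example of a measure that may vary by site.

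**The larger rates rest on strong assumptions.** This stands. Reaching 17-23% takes large site differences in both measure and response, and under mild gradients adding site lowers the rate only from 7.2% to 6.4%. Section 2.1 speaks of what may differ between centers, and this trial standardizes BIO through manuals and certified interventionists. No site difference in response is given for it.

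**Site adjustment discards information.** If patient mix truly differs between centers, part of a real predictor's signal lies between sites and is removed. This stands, and reporting an unadjusted analysis alongside would be reasonable.

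**Conclusion.** The point holds as a gap in specifying secondary analyses. Neither the predictor nor the mechanism model in Section 8.3 names a factor that the trial stratifies by, adjusts for elsewhere, and expects to be related to both patient characteristics and BIO success.

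Under assumed inputs, the false-positive rate for a measure with no within-site effect is about 7% under mild site differences and 11-23% under moderate to strong ones, against about 5-6% with site included. It needs both the measure and response to differ by site. Only false positives were examined; masking of a true predictor was not.

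A reader might also infer that the treatment comparison is compromised. It is not, because the primary efficacy model includes site and sex.

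**What to change.** In Section 8.3:

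1. Include clinical site and sex as fixed covariates in every predictor and mechanism model, as in Section 8.1.
2. When testing predictor-by-treatment interactions, add site-by-treatment as a sensitivity check.
3. For sphincter structure, add ultrasound versus MRI, which Section 4.3.8 already has sites report, where it varies within a site. Do not add a separate 2-D versus 3-D term: probe dimension is not among the items listed for reporting, and among ultrasound readings 2-D is assigned to one site, so the site term absorbs that difference. Site adjustment does not make the imaging methods interchangeable.

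Cost: analysis-plan wording, four degrees of freedom for five sites, four more in the interaction check, and some loss of between-site information about predictors. Site and imaging modality are already recorded, so no new data are needed. Evoked potentials are collected at two sites only, so a model that includes them spends one degree of freedom on site.
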